Primary objective	Assess the administration of Multigam 10% compared to Multigam 5% to shorten the infusion time without additional side effects and loss of quality of care.
Secondary objectives	
 • Evaluate the tolerability and infusion related side effects. • Evaluate patient satisfaction. • Evaluate the number of care actions required. • Evaluate nursing staff satisfaction.
Setup	
In this non-interventional, monocentric, observational study, the administration of Multigam 10% will be compared with the standard (Multigam 5%) in patients with a secondary immunodeficiency due to a hematological disorder.
 
Patients who are being treated with Multigam because of

	
their secondary immunodeficiency will be evaluated for inclusion.
 
The last administration of Multigam 5% will serve as a control. During this check, different parameters will be evaluated:
 
 -Infusion time (hours) -Hospitalization time at the oncological day clinic (hours) -Side effects (via CTCAE v4.03) -Nursing staff care actions 
Subsequently, an identical evaluation will take place at the first administration of Multigam 10% and the satisfaction of the patient and the nursing staff will also be assessed. The results will be analyzed and compared.
 
Patients can then receive Multigam 10% or Multigam 5% according to their preference.
  <pre> graph TD A[Screening] --> B["Multigam 5% administration"] B --> C["First evaluation"] C --> D["Multigam 10% administration"] D --> E["Final evaluation"] </pre>
Endpoints	
Primary:
 
To compare the infusion time (hours) and tolerance of Multigam 10% and the standard administration of Multigam 5%.

	
Secondary:
 
 • Assess the tolerance and patient satisfaction of Multigam 5% vs. Multigam 10% via: 
 - Patient questionnaire - Scoring of side effects via CTCAE v4.03 • Assess nursing staff care actions • Assess the satisfaction of the nursing staff (questionnaire) • Patient characterization (age, gender, disorder)
Population	30 patients with a secondary immunodeficiency due to a hematological disorder.
Inclusion criteria	
 • Age \geq 18 years • Secondary immunodeficiency due to a hematological disorder • Patient received at least 2x Multigam 5% • No side effects (grade 2 or higher according to CTCAE v4.03) during their last 2 Multigam 5% infusions • Patient needs at least 2x Multigam • Signed informed consent form
Exclusion criteria	
 • Patient received less than 2x Multigam 5% • Side effects (grade 2 or higher according to CTCAE v4.03) during their last 2 Multigam 5% infusions • Patient refuses to participate in the study
Maximum duration of study/treatment	
 • 2 months
Version and date of final protocol	Version 3 – 8 September 2017

2. Background and rationale

Background

The immune system ensures the detection and elimination of pathogens and even transformed cells. However, normal functioning can be disrupted by a variety of factors. Both primary and secondary causes can lead to an immune deficiency with increased vulnerability for infections (Cooper, et al. 2003, Shinen & Shearer, 2008).

Secondary immune deficiencies can be caused by various diseases (lymphoproliferative disorders, infections, ...) and therapies (immunosuppressants, anti-inflammatory drugs, ...). In lymphoproliferative disorders such as chronic lymphocytic leukemia (CLL) and multiple myeloma (MM), both treatment and the disease itself contribute to a secondary immunodeficiency. In order to strengthen the resistance in these patients, substitution therapy with immunoglobulins can be started in cases of recurrent infections (Friman, et al. 2016). Intravenous gamma globulins (IVIg) are reimbursed in Belgium for patients with CLL and MM with a secondary immunodeficiency that resulted in a life-threatening infection or in repeated episodes of clinically significant infections requiring antibiotics. The dose is 0.4 to 0.5 g / kg every 3 to 4 weeks.

At the UZ Leuven Hematology department, Multigam is being used as standard IVIg substitution therapy. Multigam is an immunoglobulin preparation that is produced from the plasma of human donors. It exists in both 5% and 10% concentrated solution and is administered intravenously.

Rationale

The day clinic of the Hematology department at UZ Leuven is experiencing a yearly growth of about 5% in the number of patient contacts. For this reason, we are constantly looking for ways to shorten the time spent at the day clinic to create additional capacity without causing a loss of quality in care. With the arrival of Multigam 10%, patients will be able to switch to this new immunoglobulin solution. This allows patients to be treated independently of the dose and their weight within a shorter period of time.

With this study we want to quantify the transition from Multigam 5% to Multigam 10% in a scientific way. The rationale of this study is to compare and evaluate the administration of both solutions in terms of infusion time, infusion related side effects, patient satisfaction, number of care actions and satisfaction of the nursing staff, and this in about 30 patients.

3. Study objectives and design

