3.5 Study diagram

3.6 Study flowchart

	Study visit 1 (Multigam 5%)	Study visit 2 (Multigam 10%)
Information and consent form	X	
Physical examination AE scoring via CTCAE (v4.03)	X	X
Patient questionnaire		X
Questionnaire concerning IVIg administration	X	X
Nursing staff questionnaire		X

4. Selection and exclusion of participants

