4.3 Expected duration of study

- Start-up: february 2017
- Recruitment: 4 weeks
- First participant: Q2 2017
- EC submission: Q2 2017
- Final reporting: december 2017

5. Study actions per visit

5.1 Study visit 1

- Sign information and consent form
- Multigam 5% administration
- Questionnaire concerning IVIg administration
- CTCAE v4.03 scoring during and after infusion

5.2 Study visit 2

- Multigam 10% administration
- Questionnaire concerning IVIg administration
- CTCAE v4.03 scoring during and after infusion
- Patient questionnaire
- Nursing staff questionnaire

6. Data collection

The following data will be stored in the eCRF:

- Patient characteristics (age, gender and disorder)
- Infusion time (hours)
- Hospitalization time at the oncology day center (hours)
- Safety reporting (collect AEs en SA's according to CTCAE v4.03 criteria)
- Questionnaire concerning IVIg administration (both visits, annex 2)
- Patient satisfaction questionnaire (last visit; annex 1)
- Nursing staff satisfaction questionnaire (last visit; annex 3)

7. Assessment of efficiency

Primary endpoint:

- **Comparing the infusion time and tolerance**

Evaluate via time measurements, questioning and AE reporting during both treatments

Secondary endpoints:

- **Satisfaction and therapeutic tolerance**
 - Evaluation of satisfaction via questionnaire and tolerance via AE reporting
- **Safety**
 - Evaluate AEs and SAEs via CTCAE v4.03 criteria
- **Care actions**
 - Evaluate the number of nursing actions per patient
- **Satisfaction of nursing staff**
 - Evaluation of satisfaction via questionnaire
- **Patient characterization**
 - Characterization of patients (age, gender, disorder)

8. Assessment of safety

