8.2.1.5 Reporting procedure

All AEs are bundled into the eCRF starting from the patient having signed the information and consent form up to and including the last study visit.

All AEs considered to be related to the substitution therapy and all SAEs independent of their relationship must be followed up until they recover, recover with consequences, non-recovery (death by other cause) or death (by the SAE).

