Annex 1: Patient questionnaire

	Strongly disagree (1)	Disagree (2)	Neutral (3)	Agree (4)	Strongly agree (5)
I experienced fewer side effects with Multigam 10%					
I experienced time gain with Multigam 10%					
I will therefore have a more productive day					
For my own situation I am in favor of using Multigam 10%					

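### Patient satisfaction is declared as a 5% versus 10% comparison, but it is measured only by statements worded towards 10%, and the choice offered afterwards is not recorded

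*Combined protocol and SAP*

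**What the plan says.** The Synopsis (Endpoints) lists as a secondary endpoint: "Assess the tolerance and patient satisfaction of Multigam 5% vs. Multigam 10% via" a patient questionnaire and CTCAE scoring. Section 3.3 repeats the 5% versus 10% comparison.

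The questionnaire is given once. The flowchart in 3.6 marks it only under visit 2, and section 6 lists it as "Patient satisfaction questionnaire (last visit; annex 1". The parameters that the Synopsis (Setup) names for the 5% control infusion do not include satisfaction.

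Annex 1 has four statements on a five-point scale from strong disagreement to strong agreement. They cover fewer side effects, time gain, a more productive day as a result, and the overall view: "For my own situation I am in favor of using Multigam 10" (the 10% solution). Section 9.2 plans descriptive statistics for satisfaction.

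The Synopsis (Setup) then adds: "Patients can then receive Multigam 10% or Multigam 5% according to their preference".

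**The concern.** A comparative endpoint needs an instrument on which a patient can come out for either product or for neither. Annex 1 asks only how far the patient agrees with claims made for 10%. No statement is worded for 5%, there is no neutral question about which product is preferred, and 5% receives no rating of its own at visit 1 from which a within-patient difference could be formed.

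The plan nevertheless describes a moment at which each patient may choose between the two products, and makes no use of it.

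At stake is what the report can say about patients' views. With Annex 1 alone it can give the share agreeing with statements that favour 10%. It cannot give the shares preferring 10%, preferring 5% and having no preference. Section 2 (Rationale) says that the study is meant to quantify the transition between the products and that the clinic wants shorter stays, so a result that could clearly have gone either way would carry more weight.

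**Working it through.** No planned figure bears on this point. Section 9.1 sets 30 patients without alpha, power, effect size or expected rate, so there is nothing to reproduce. The check traces the choice through the plan and then shows what the proposed item could report.

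**1. Where the choice would have to appear**

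| Place | Content | Choice recorded or used? |
|---|---|---|
| 3.6 Flowchart | Two visits; the last is the 10% infusion | No |
| 5.2 Visit 2 actions | Infusion, administration form, CTCAE, two questionnaires | No |
| 6, list under "The following data will be stored in the eCRF" | Patient characteristics, infusion time, hospitalization time, safety, administration form, patient and nursing questionnaires | No |
| 3.3 and 7, secondary endpoints | Satisfaction, tolerance, safety, care actions, nursing satisfaction, patient characterization | No |
| 9.2 Analysis | t-tests for times and care actions; descriptive for satisfaction | No |

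Adverse-event capture also ends at visit 2: section 8.2.1.5 collects events "up to and including the last study visit". No later contact is planned at which the choice could be noted.

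**2. What the overall Annex 1 item can tell apart**

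| Patient's actual view | Truthful answers to the overall item | Answer to a balanced item |
|---|---|---|
| Prefers 10% | Agree or Strongly agree | 10% |
| Content with either | Agree, Neutral or Disagree | No preference |
| Prefers 5% | Disagree, possibly Neutral | 5% |

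The middle row overlaps both others. Someone content with either product can truthfully be in favour of 10% without preferring it.

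The side-effect statement, "I experienced fewer side effects with Multigam 10" (again the 10% solution), has the same weakness. Disagreement covers both the same number of side effects and more. Eligibility leaves little room for fewer: the Synopsis bars grade 2 or higher effects in the last two 5% infusions, and section 4.1 bars any. The remaining two statements concern time and its consequence, so the overall verdict rests on one item.

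**3. What a balanced item would report**

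The exact (Clopper-Pearson) 95% interval for x of n runs from the 2.5% quantile of Beta(x, n − x + 1) to the 97.5% quantile of Beta(x + 1, n − x). Take n = 30 (section 9.1), assuming that all answer. The counts are assumptions, because the documents give none.

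| Stating 10% | Proportion | Exact 95% interval |
|---|---|---|
| 15/30 | 50% | 31.3% to 68.7% |
| 18/30 | 60% | 40.6% to 77.3% |
| 20/30 | 67% | 47.2% to 82.7% |
| 21/30 | 70% | 50.6% to 85.3% |
| 24/30 | 80% | 61.4% to 92.3% |
| 27/30 | 90% | 73.5% to 97.9% |

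For 24/30 the limits are the 2.5% quantile of Beta(24, 7) and the 97.5% quantile of Beta(25, 6). Precision is coarse: at 15/30 the interval reaches 68.7 − 50 = 18.7 points either side. The smallest count whose interval excludes 50% is 21 (two-sided exact p = 0.043). Fifty percent is a natural reference only among patients who name a product; once some answer no preference, the three proportions should be shown together.

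**The case against.** The strongest reply is that the plan promises satisfaction, not preference. Annex 1 is a satisfaction questionnaire reported descriptively, and the sentence about choice can be read as a return to routine prescribing after a non-interventional study. This stands. A reader might infer that a promised outcome is not being collected; the documents do not support that, because no objective, endpoint or analysis names preference. What remains is that the declared endpoint is itself comparative and its instrument faces one way.

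Second, the scale permits disagreement. A reader might infer that only agreement can express a view. That is too strong: every patient has already had 5%, and someone who disagrees with the overall item is rejecting 10% for their own use. The narrower point survives, that Neutral and disagreement do not identify a preference for 5%.

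Third, a reader might infer that the actual choice is available at no cost. It is not. Eligibility requires a need for only two or more Multigam infusions, so a third is not assured. With the 3-to-4-week interval given in the Background, the product next received is known only after the last study visit. Routine records may hold it, but no extraction is planned. A field at visit 2 captures a stated intention.

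Fourth, the new item would be answered in the same day clinic, after a single 10% infusion, by patients selected for tolerating 5%. This also stands: balanced wording reduces the pull towards 10% but does not remove it.

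**Conclusion.** The point holds as a modest, optional improvement. The satisfaction endpoint is framed as 5% versus 10%, its only patient instrument is worded towards 10% and used once, and the choice mentioned in the Synopsis is neither recorded nor analysed. As planned, the study cannot report a two-sided result on that endpoint.

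The effect is confined to one descriptive secondary endpoint. No planned number changes, and the comparisons of infusion time and tolerance are untouched.

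The size of any bias is unknown. One could assume that 10% to 20% of patients drift from Neutral to Agree and conclude that 3 to 6 of 30 would be miscounted (0.10 × 30 = 3; 0.20 × 30 = 6). Nothing in the documents supports such a rate, so no count should be attached to it. The intervals above show only the precision available from 30 answers, not a prediction for this study.

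**What to change.** Add one item to the visit 2 patient questionnaire and the eCRF: *preferred product for further infusions: 5% / 10% / no preference*, with the main reason (time, side effects, other). List it under patient satisfaction in 3.3 and add it to the data list in section 6. In 9.2, state that the number and proportion in each category will be reported with exact 95% intervals, using the patients who answer as denominator. Label the result as preference stated after one 10% infusion, not as the product actually received. Keep the Annex 1 statements as supportive information.

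The cost is one extra item and a sentence each in 3.3, 6 and 9.2, with no added visit and no change to treatment. The remaining limitation, that answers are given in the day clinic, should be acknowledged in the report.

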3.1 Study objectives

With this study we want to evaluate the administration of Multigam 10% compared to the standard (Multigam 5%). We want to observe whether there are changes in infusion time and infusion related side effects. In addition, the patient satisfaction, the number of care actions and the satisfaction of the nursing staff will also be evaluated.

3.2 Primary endpoints

Comparing the infusion time (hours) and tolerance between Multigam 10% and the standard administration.

[figure not shown]
3.3 Secondary endpoints

- Assess the satisfaction and therapeutic tolerance of Multigam 5% vs. Multigam 10% via:
 - Patient questionnaire
 - CTCAE v4.03
- Assess the care actions of the nursing staff
- Assess the satisfaction of the nursing staff (questionnaire)
- Patient characterization (age, gender, disorder)

3.4 Study design

Prospective - Observational

3.5 Study diagram

3.6 Study flowchart

	Study visit 1 (Multigam 5%)	Study visit 2 (Multigam 10%)
Information and consent form	X	
Physical examination AE scoring via CTCAE (v4.03)	X	X
Patient questionnaire		X
Questionnaire concerning IVIg administration	X	X
Nursing staff questionnaire		X

4. Selection and exclusion of participants

4.1 Inclusion criteria

- Age \geq 18 years
- Secondary immunodeficiency due to a hematological disorder
- Patient received at least 2x Multigam 5%
- No side effects during their last 2 Multigam 5% infusions
- Patient needs at least 2x Multigam
- Signed informed consent form

4.2 Exclusion criteria

- Patient received less than 2x Multigam 5%
- Side effects/intolerance for Multigam 5%
- Patient refuses to participate in the study

4.3 Expected duration of study

- Start-up: february 2017
- Recruitment: 4 weeks
- First participant: Q2 2017
- EC submission: Q2 2017
- Final reporting: december 2017

5. Study actions per visit

5.1 Study visit 1

- Sign information and consent form
- Multigam 5% administration
- Questionnaire concerning IVIg administration
- CTCAE v4.03 scoring during and after infusion

5.2 Study visit 2

- Multigam 10% administration
- Questionnaire concerning IVIg administration
- CTCAE v4.03 scoring during and after infusion
- Patient questionnaire
- Nursing staff questionnaire

6. Data collection

The following data will be stored in the eCRF:

- Patient characteristics (age, gender and disorder)
- Infusion time (hours)
- Hospitalization time at the oncology day center (hours)
- Safety reporting (collect AEs en SA's according to CTCAE v4.03 criteria)
- Questionnaire concerning IVIg administration (both visits, annex 2)
- Patient satisfaction questionnaire (last visit; annex 1)
- Nursing staff satisfaction questionnaire (last visit; annex 3)

7. Assessment of efficiency

Primary endpoint:

- **Comparing the infusion time and tolerance**

Evaluate via time measurements, questioning and AE reporting during both treatments

Secondary endpoints:

- **Satisfaction and therapeutic tolerance**
 - Evaluation of satisfaction via questionnaire and tolerance via AE reporting
- **Safety**
 - Evaluate AEs and SAEs via CTCAE v4.03 criteria
- **Care actions**
 - Evaluate the number of nursing actions per patient
- **Satisfaction of nursing staff**
 - Evaluation of satisfaction via questionnaire
- **Patient characterization**
 - Characterization of patients (age, gender, disorder)

8. Assessment of safety

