9.1 Sample size

For this descriptive, semi-quantitative study, the sample size is determined on 30 patients. Based on data in the package leaflet, we expect that the infusion time for Multigam 10% will be shorter than for Multigam 5%. This sample size will also be sufficient to correct for any variability as a result of nursing activities. A sample of 30 patients is sufficient to detect mild side effects. If, unexpectedly, more side effects occur with Multigam 10% administration, we will extend the sample size through an amendment and investigate this further. To evaluate the satisfaction of the patients and the nursing staff, 30 patients are also sufficient to correct for any missing values.

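### Side-effect observation has no fixed end and stops with the 10% visit, so the 10% product can be watched for less time than the 5% product on a primary endpoint

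*Combined protocol and SAP*

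**What the plan says.** - Sections 5.1 and 5.2 list the same safety item at the 5% visit and the 10% visit: "CTCAE v4.03 scoring during and after infusion". Neither gives a number of hours, a discharge rule or a later contact.
- Section 3.2 makes tolerance part of the primary endpoint: "Comparing the infusion time (hours) and tolerance between Multigam 10% and the standard administration". Section 7 describes its assessment as "Evaluate via time measurements, questioning and AE reporting during both treatments".
- Section 8.2.1.5 collects adverse events in the eCRF "starting from the patient having signed the information and consent form up to and including the last study visit". Visit 2, the 10% infusion, is the last study visit.
- The rationale in Section 2 seeks "ways to shorten the time spent at the day clinic to create additional capacity", and Section 9.1 expects a shorter infusion with the 10% product.
- Section 8.2.1.3 records start and stop of an adverse event as dates. Annex 2 has clock times for the start and stop of the infusion but none for a reaction.
- Section 9.2 names tests for care actions, infusion time and hospitalization time. It names no analysis of side effects and no allowance for unequal observation time.

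**The concern.** The study asks whether the infusion can be shortened without adding side effects. The time during which side effects can be seen is tied to the infusion and the stay, which are the quantities that the 10% product is meant to reduce. If scoring in practice ends when the patient leaves, a reaction starting some hours after the start could fall inside a long 5% visit and outside a short 10% visit.

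The general adverse-event window leans the same way. A reaction at home after the 5% infusion can still be reported at visit 2, while one at home after the 10% infusion has no later visit. Limiting the comparison to infusion-day events would remove this second inequality but leave the first.

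Two things depend on the count. One is the tolerance conclusion itself. The other is the safeguard in Section 9.1, under which the sample is extended only if more side effects appear with the 10% product. Under-counting on 10% would blunt that trigger.

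**Working it through.** **Figures in the plan.** There is nothing to reproduce. The documents give no infusion time, length of stay, reaction rate or onset distribution, and the 30 patients in Section 9.1 are not derived from a rate. Every numerical input below is an assumption except the 30 patients and the 3-week interval in step 4.

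**Step 1: infusion-day window, uniform clock-time onset.** Let the true risk be p on both products, with onset uniform over H hours from infusion start. Let the infusion last T hours and the stay afterwards s hours. If scoring ends with the stay:

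- observed risk = p × (T + s) / H
- ratio of 10% to 5% = (T10 + s) / (T5 + s), so p and H cancel.

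Central case (p = 20%, H = 6 h, s = 0.5 h, T5 = 4 h, T10 = 2 h):

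- 5% product: 0.20 × 4.5/6 = 15.0%, or 4.5 of 30 patients
- 10% product: 0.20 × 2.5/6 = 8.3%, or 2.5 of 30 patients
- ratio 2.5/4.5 = 0.556, which is 44% lower with no true difference.

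Range over T5 = 3–4 h, T10 = 1.5–2.5 h and s = 0.5–1 h:

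- smallest: 3 h against 2.5 h with s = 1 h gives 3.5/4 = 0.875, or 12.5% lower
- largest: 4 h against 1.5 h with s = 0.5 h gives 2/4.5 = 0.444, or 56% lower.

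In absolute terms the gap depends on p. At p = 5%, the central case gives 30 × 0.05 × 4.5/6 = 1.1 against 30 × 0.05 × 2.5/6 = 0.6 expected patients.

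**Step 2: a different clock-time model, varying the end of scoring.** Let onset be exponential with mean m hours from infusion start, and let scoring stop a hours after the infusion ends. The share captured is 1 − exp(−(T + a)/m). With T5 = 4 h, T10 at 50% or 75% of that, and m from 1 to 24 h:

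| Scoring after infusion end | Capture ratio, 10% to 5% |
|---|---|
| 0 h | 0.52–0.97 |
| 0.5 h | 0.58–0.98 |
| 2 h | 0.69–1.00 |
| 24 h | 0.96–1.00 |
| 72 h | 0.996–1.00 |

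Example with 20% risk, 30 patients (30 × 0.20 = 6 true reactions), 4 h against 2 h, a = 0.5 h and m = 4 h: 6 × (1 − exp(−4.5/4)) = 4.05 against 6 × (1 − exp(−2.5/4)) = 2.79 expected events.

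**Step 3: onset that follows the infusion.** If reactions arise during the infusion whatever its length, or at a given delay after its end with the same a at both visits, the same share is captured on both products. The ratio is 1.

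**Step 4: the window in Section 8.2.1.5.** Suppose a share f of reactions occurs during infusion and the rest are delayed, exponentially with mean 12–24 h after its end. After 5%, collection runs to visit 2; the schedule in Section 2 is every 3 to 4 weeks, so take 21 days, and capture is practically complete. After 10%, it runs 0–2 h. Capture on 10% is f + (1 − f) × (1 − exp(−a/m)).

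| Share during infusion | Capture ratio, 10% to 5% |
|---|---|
| 30% | 0.30–0.41 |
| 60% | 0.60–0.66 |
| 90% | 0.90–0.92 |

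This inequality does not need clock-time onset. It needs only some delayed reactions, reported at visit 2 and counted against 5%.

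**Step 5: can it be repaired from the data?** Infusion start and stop and hospitalization time are collected, so the length of each on-site window can be approximated. Without the clock time of onset, a reaction cannot be placed inside or outside a common window.

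**The case against.** The strongest reply is that the plan does not end scoring at discharge. The wording covers a period after infusion without limit, and Section 8.2.1.5 keeps adverse events in scope beyond the infusion day. This stands against the inference that side effects are captured only while the infusion runs. It does not restore balance, because that wider window closes with the 10% visit. The further rule in Section 8.2.1.5 on following events until they resolve applies to events already known and does not find new ones.

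Second, a reader might infer that a shorter infusion necessarily makes the 10% product look better tolerated. The documents do not support that for infusion-day scoring. It requires scoring that stops at or soon after discharge and onset that follows the clock, and the plan states neither. Step 3 shows no bias when onset follows the infusion, and step 2 shows little when scoring lasts 24 h or more.

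Third, a reader might infer that the tolerance comparison as a whole is biased in favour of 10%. That cannot be concluded either. Patients must have had no side effects in their last two 5% infusions (Section 4.1; the synopsis says none of grade 2 or higher). This may make the 5% control unusually clean and so act against 10%. It also makes a 20% risk on 5% look high, and at 5% risk the central gap is about half a patient. These points limit size and certainty. They do not make the observation times equal, and two biases of unknown size cannot be relied on to cancel.

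**Conclusion.** The concern holds in a conditional form. The plan as written can observe the 10% product for less time than the 5% product on a primary endpoint, through an infusion-day window with no fixed length and through adverse-event collection that ends with the 10% visit. Date-only onset means the data could not be cut to equal windows afterwards.

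Under uniform clock-time onset and the infusion and stay lengths assumed above, the infusion-day effect alone would make 10% look about 12–56% better with no true difference. It falls to nil if onset follows the infusion, and to at most about 4% if scoring runs 24 h after the infusion (ratio 0.96–1.00 in step 2). The inequality from Section 8.2.1.5 can be larger if many reactions are delayed. The net direction of error in the tolerance comparison cannot be determined from the documents.

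**What to change.** 1. Add the clock time of onset to the adverse-event record.
2. In Sections 5.1 and 5.2, replace the open-ended scoring period with the same fixed number of hours from infusion start at both visits, completed by a brief call if the patient has left.
3. Make the same follow-up contact after each infusion, and extend collection in Section 8.2.1.5 past visit 2 to that contact, so that late reactions have the same chance of being reported on both products.
4. State in Section 9.2 that tolerance is compared over this common period.

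If no call is wanted, report tolerance twice: over the full stay, and over the shorter of each patient's two observation windows, counted from infusion start. The second is the equal-time comparison if onset follows the clock. The first is fair if onset follows the infusion and the stay afterwards is similar. State also that late reactions on the 10% product are not observed. The onset time is needed for this option too.

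The cost is one extra field, plus either a brief call per infusion or one extra table. With the table, the two counts may disagree and both must be shown. No treatment or clinical rule changes.

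### Patient satisfaction is framed as 5% versus 10%, but it is rated only once, after 10%, on four items all worded in favour of 10%

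*Combined protocol and SAP*

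**What the plan says.** Two places frame patient satisfaction as a comparison of products. The synopsis has "Assess the tolerance and patient satisfaction of Multigam 5% vs. Multigam 10% via" a patient questionnaire and CTCAE scoring. Section 3.3 has "Assess the satisfaction and therapeutic tolerance of Multigam 5% vs. Multigam 10% via" the same two instruments.

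The patient questionnaire is scheduled at visit 2 only. This is stated in the flowchart (Section 3.6), in the visit 2 list (Section 5.2) and in the data list (Section 6: "Patient satisfaction questionnaire (last visit; annex 1"). The synopsis setup is consistent with this: at the first 10% administration the evaluation done for 5% is repeated and "the satisfaction of the patient and the nursing staff will also be assessed".

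The one questionnaire used at both visits is the nursing form (Section 6: "Questionnaire concerning IVIg administration (both visits, annex 2"). Annex 2 shows that it holds infusion start and stop times and a count of care actions.

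Annex 1 has four items on a 1 to 5 agreement scale. They cover fewer side effects with 10%, time gained with 10%, a more productive day as a result, and being in favour of 10% for oneself. Section 9.2 plans descriptive statistics for satisfaction.

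After the study infusions, the synopsis says "Patients can then receive Multigam 10% or Multigam 5% according to their preference". Neither the flowchart nor Section 6 lists that choice as data.

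**The concern.** A comparison of satisfaction between two products is most convincing when each is rated at the time it is given, with the same questions. Here 10% is rated on the day, while 5% enters only through the patient's memory of it. The patient knows which product is which, and every statement names or implies a benefit of 10%.

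What is at stake is the ability to detect a worsening. The primary objective is a shorter infusion without more side effects and without loss of quality of care. Patient satisfaction is one of the few measures in the plan that could reveal such a loss from the patient's side. A form that offers only degrees of agreement with favourable statements is poorly suited to that. High agreement would also be hard to separate from courtesy or imperfect recall.

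**Working it through.** The plan gives no figure for this endpoint beyond the 30 patients in Section 9.1, which comes with no effect size, SD, alpha or power. There is thus no calculation to reproduce. The check sets the texts side by side and then sizes the remedy.

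**1. What is collected at each visit (Sections 3.6, 5.1, 5.2 and 6; Annexes 1 and 2)**

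| | Visit 1 (5%) | Visit 2 (10%) |
|---|---|---|
| Infusion time, care actions (Annex 2) | yes | yes |
| CTCAE scoring | yes | yes |
| Patient satisfaction (Annex 1) | no | yes |

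Patients with a contemporaneous 5% satisfaction score: 0 of 30.

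**2. What the Annex 1 items can show**

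- Items 1 and 2 (side effects, time) ask for a relative judgement in which only improvement on 10% is stated. A patient who found the two products equal and one who found 10% worse should both disagree.
- Item 3 (productive day) is tied by *therefore* to the time gain. A patient who noticed no gain has no clear way to answer.
- Item 4 is a stated preference for 10%. Disagreement does not say whether the patient prefers 5% or is indifferent, although the neutral category may take some of the latter.
- No item asks for overall satisfaction with either product.

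All 4 of 4 items therefore point towards 10%.

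**3. What the plan can yield as written**

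It yields a one-sample proportion agreeing with each statement. Assuming 30 complete answers, the exact (Clopper-Pearson) 95% CIs at three assumed agreement rates are:

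- 15/30 = 50%: 31% to 69%
- 21/30 = 70%: 51% to 85%
- 27/30 = 90%: 73% to 98%

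**4. What a neutral form at both visits would yield**

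Half-width of the 95% CI for the mean paired change, in units of its SD, with n = 30:

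t(0.975, 29) / √30 = 2.045 / 5.477 = 0.373.

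The documents give no SD for such a change, so this cannot be fixed in scale points. Each point of SD contributes about 0.37 points of half-width.

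**5. What recording the intended product would yield**

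Half-width at a proportion of 50%, normal approximation: 1.96 × √(0.25/30) = 1.96 × 0.0913 = 0.179, or about 18 percentage points. The exact interval in step 3 (31% to 69%) has about the same width.

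**The case against.** The strongest reply is that the comparison is already in the questions. Annex 1 asks patients to judge 10% against what they had before, and eligible patients have received at least two 5% infusions. A direct comparative rating after both products is a recognisable method. Section 9.2 asks only for descriptive statistics, which can be produced in full. This stands, and it limits the point.

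Several stronger readings are tempting, and the documents do not support them:

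- *That the endpoint cannot be computed.* A reader might infer this from the lack of a 5% score. But no section defines the endpoint as a paired or within-patient score; it is to be assessed through the questionnaire, and a perceived comparison can be reported.
- *That the nursing questionnaire has the same mismatch.* It too is given only at the last visit ("Nursing staff satisfaction questionnaire (last visit; annex 3"), but its endpoint reads "Assess the satisfaction of the nursing staff (questionnaire", with no 5% versus 10% framing.
- *That recall spans exactly 3 to 4 weeks.* That is the dosing interval in the Background. No gap between the visits is stated, so the recall period is an inference.
- *That preference goes unmeasured.* Item 4 records a stated preference. What is not recorded is the product the patient goes on to use.

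It is also fair to say that a form at both visits would not remove courtesy or novelty effects, because the order is fixed and nothing provides for blinding. Time and adverse events are already recorded at both visits, so neutral items on those topics overlap with existing data. The main gain is in overall satisfaction. A side-effect item also has little room to improve, since eligibility screens out recent side effects on 5% (any in Section 4.1; grade 2 or higher in the synopsis).

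What survives is the wording of the items and the missing contemporaneous 5% rating. The comparative format does not answer either.

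**Conclusion.** The point holds in a limited form. The endpoint is framed as 5% versus 10%, but the 5% side is supplied only by recall, in a single unblinded rating after 10%. The items can show perceived benefit. They cannot show a loss of satisfaction as distinct from no change, which is the finding that would bear on quality of care.

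This concerns one descriptive secondary endpoint. Infusion time and care actions are recorded at both visits and are unaffected. The case for acting rests on the remedy being cheap: it would replace no contemporaneous 5% ratings with up to 30 pairs and a half-width of about 0.37 SD of the change. That figure assumes all 30 patients complete both forms; missing pairs would widen it.

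**What to change.** 1. At visit 1 after 5% and at visit 2 after 10%, give the same few product-neutral items on the existing 1 to 5 scale, including one on overall satisfaction. Report the paired change descriptively with its 95% CI.
2. Keep the comparative items at visit 2 as a supplement, with balanced options (better with 10%, the same, worse with 10%). Remove the presupposed time gain from item 3.
3. At the end of visit 2, record which product the patient states they will continue with, and report the proportion with its 95% CI. Taking the stated intention at that visit avoids follow-up beyond the study.
4. Update Sections 3.3, 3.6, 5.1, 6 and 9.2, the synopsis and Annex 1 to match.

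If no visit 1 form is added, restate the endpoint as perceived change and preference after 10%, and still balance the response options.

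The cost is a few minutes per patient at a visit that already includes consent, CTCAE scoring and a nursing form, plus one short form and one eCRF field. The fixed order and the lack of blinding remain, and the report should say so.
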